## CSE vs. Epidural for Postpartum Depression NCT03022526 July 15, 2020

## STUDY PROTOCOL:

The clinical procedure that will be used for research purposes is labor epidural analgesia initiation by combined spinal-epidural (CSE) or epidural (E).

Study participants, prior to enrollment, will have already made a decision for themselves to use labor epidural analgesia to manage pain during labor (decision made is one eligibility criteria). The study intervention, CSE or E, are both commonly used techniques in the initiation of epidural analgesia, but currently the utilization of one or the other of these strategies is left to the discretion of the anesthesia clinician and is dictated primarily by clinician preference. Thus an RCT will address this level of bias. Both CSE and E can be considered the standard of care for any laboring woman requesting labor epidural analgesia.

BASELINE: At the first encounter, an assessment will include measurements of depression (EPDS), anxiety (STAI inventory), resiliency (ER 89), pain catastrophizing (PCS), perceived social support (MSPSS) and pain (BPI-long form). For women recruited at the 3rd trimester visit, Quantitative sensory testing (QST) will be performed. The pain sensitivity test will involve the use of a small pad attached to the participant's arm. The thermal device will gradually heat up from the moment the participant feels the heat until the pain sensation becomes uncomfortable; the participant is instructed to tell investigators when to discontinue the test at the first moment of discomfort, at which time the test is stopped. The pain sensitivity test also includes pressure devices to assess pressure pain. These devices are widely and commonly used in clinical pain research. From these test, we will determine the participant's sensitivity profile which we will use in our study analysis.

To enhance recruitment, we will also approach women in early labor who have not yet received an epidural after consultation with their bedside nurse and once it has been established that they meet eligibility criteria. These women will answer the aforementioned baseline surveys but will not participate in QST.

Upon hospital admission for labor and delivery: confirmation of term (>/= 37 weeks) planned vaginal delivery will occur. The participant will be randomized to one of two groups: combined spinal-epidural (CSE) or epidural (E). Randomization will occur by block allocation. At the moment of patient request for labor epidural analgesia, one sealed and opaque envelope containing the next assignment group will be opened. The envelopes will be located in a designated location in the anesthesia workroom of the birth center, and thus no delays in the laboring person's ability to receive the requested epidural is anticipated. Should any delay occur for any reason, no randomization will occur and the patient will receive the epidural per routine request and clinical flow. Initiation of each labor analgesic strategy will be standardized to minimize variability of analgesia, and is outlined on the study figure attached. Management of breakthrough pain will be standardized and will occur by the strategy outlined on the study figure attached ("supporting documentation").

Throughout labor, pain will be assessed hourly using 100mm visual analog scales for both pain intensity and pain unpleasantness. Regardless of onset of labor (spontaneous or induction), hourly assessments are required to measure with accuracy and density the change in pain that is

CSE v. Epidural for Postpartum Depression

experienced over time for women in labor, in response to both the progress of labor and any changes in response to medications via the epidural infusion. For the entire labor, labor variables will be recorded, including sterile vaginal exam (SVE) at the time of epidural request, duration of labor (time from admission to unit until time of delivery), number of manual epidural supplemental doses, total dose of local anesthetic and epidural opioid required, and the outcome of labor -- both maternal (normal spontaneous vaginal delivery, instrumental delivery, cesarean delivery, perineal lacerations, total oxytocin dose requirements) and neonatal (sex, Apgar scores, need for resuscitation, need for neonatal ICU). Study procedures will continue should the need arise for a cesarean delivery or if there are any other complications to the pregnancy/fetus.

Postpartum measurements will be made as follows:

Postpartum day 0-2: Within 2 days we will measure co-variates of pain (BPI short), breastfeeding (yes/no) and perceived stress (PSS).

At 6 weeks, we will measure the primary outcome of EPDS score as well as co-variates including pain (BPI short), maternal infant attachment (MPAS), parenting self-efficacy (PMP-SE), child development (ASQ-3), and breastfeeding (yes/no) (i.e. "Are you currently breasfteeding? Yes or no.") A margin of 7 days around the 6 week postpartum mark will be allowed for the patient to respond.

At 3 months, we will assess breastfeeding (Y/N), Depression (EPDS), Pain (BPI – Short Form), Mother-infant attachment (MPAS), Parenting self-efficacy (PMP-SE), Child development (ASQ-3). A margin of 7 days around the 3 month postpartum mark will be allowed for the patient to respond.

Should a participant not respond to follow-up surveys at the specified time, we will exclude their data from analysis; depending upon the volume and nature of such missing data, we reserve the ability to impute missing data if MAR or MNAR.

Interactions with participants will occur in person, electronically (email), or by phone. Investigators will consent participants to retain the ability to re-contact participants at a future date for follow-up questions.

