## STATISTICAL ANALYSIS PLAN:

The estimated incidence of PPD in U.S. American women is 20%, commensurate with estimates of institutional rates of PPD at Magee-Womens Hospital.36 As a pilot, we will target 10% of the sample required for a full study. The primary outcome is risk for PPD, measured by EPDS score at the 6-week postpartum visit. A sample of 394 participants, 197 in each group, will have 80% power to detect a 10% reduction in PPD symptoms at a significance level of 5% (two-tailed). With an optimistic estimated attrition of 15%, a full trial would aim to enroll 454 participants, 227 in each group. For this pilot we will target a sample of 23 patients in each group (total 46), to yield 10% of the full study sample. Given a yet unknown attrition rate, we estimate that study procedures in a maximum of 60 participants in each group will be the maximum number of participants necessary to establish a clear protocol. We will review and refine the protocol every 5 patients until no further changes to the protocol are made over 5 consecutive participants. We will prospectively gather data on screening eligibility, consent and decline rates, crossover rates, and provider and subject feedback.

Linear regression will be used to examine the relationship between EPDS scores and treatment group, both over time in participants and by group. The relationship between pain and EPDS will also be examined using linear regression. T-tests, linear regression, and chi-squared tests will be used, where appropriate, to examine the relationships between treatment group and pain, infant attachment, infant development, and breastfeeding.

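### The pain comparison between groups specifies no baseline pain term, although every woman completes a BPI before allocation; naming one in a regression model is a cheap, modest gain in precision.

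*Combined protocol and SAP*

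**What the plan says.** **Baseline (STUDY PROTOCOL, baseline paragraph).** The first-encounter battery includes "perceived social support (MSPSS) and pain (BPI-long form". Women first approached in early labor answer the same surveys and skip only the sensory testing. Allocation happens later, when the woman requests the epidural, so every participant has a pre-allocation BPI.

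**Follow-up (STUDY PROTOCOL, postpartum measurements).** All three postpartum assessments use the short form:
- Day 0-2: "Within 2 days we will measure co-variates of pain (BPI short".
- 6 weeks: "co-variates including pain (BPI short".
- 3 months: "we will assess breastfeeding (Y/N), Depression (EPDS), Pain (BPI – Short Form".

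**Analysis (STATISTICAL ANALYSIS PLAN, last paragraph).** "T-tests, linear regression, and chi-squared tests will be used, where appropriate, to examine the relationships between treatment group and pain", with attachment, infant development and breastfeeding in the same sentence. No model terms are given for the regression option. No BPI score is named, and nothing says how the long and short forms are to be aligned.

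**Other baseline pain information.** The sensory-testing result is promised a role: "we will determine the participant's sensitivity profile which we will use in our study analysis". It exists only for women recruited in the third trimester, and no model is stated.

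**The concern.** A pre-allocation measure of the same construct as the outcome is usually the first covariate to consider in a randomised comparison. Here it is collected from everyone, so using it requires no further data. If the analyst takes the t-test option, that information is discarded and the interval for the pain difference is wider than it need be whenever baseline and follow-up pain are correlated. The pilot targets 23 women per group, so precision is already scarce.

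Two features make the wording matter more. The choice among tests is left to what proves appropriate, so both the test and any covariates could be settled after the data are seen. And the baseline is not homogeneous: some women report pain in the third trimester, others in early labor. A baseline term entered without regard to recruitment route would put those two kinds of report on one scale as if they were equivalent.

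**Working it through.** **1. The plan's own figure.** The only powered figure is 394 women (197 per group) for postpartum depression on the EPDS at 6 weeks. Reading the 10% reduction as absolute (20% versus 10%), the unpooled formula gives n = (1.960 + 0.842)² × (0.20×0.80 + 0.10×0.90) / 0.10² = 196.2, hence 197 per group. It reproduces, but it says nothing about pain, for which no power figure is given.

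**2. Inputs for the pain comparison.**
- From the STATISTICAL ANALYSIS PLAN: 23 per group (46 in total), at most 60 per group, two-sided 5%. The 80% power is carried over from the depression calculation.
- Not in the documents, so assumed: the correlation r between baseline and follow-up BPI, taken over a range. No SD is given, so differences are in SD units.

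**3. Formulae**, with n per group and q covariates.
- Unadjusted t-test: variance of the difference = 2/n, df = 2n − 2.
- Regression on group plus covariates: variance = (2/n) × (1 − r²) × [1 + q/(2n − q − 3)], df = 2n − 2 − q. The bracket is the cost of chance imbalance in the covariates.
- Detectable difference: the value giving 80% power under the noncentral t distribution.

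**4. Results with baseline BPI as the one covariate (q = 1).**

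| Per group | t-test | r = 0.1 | r = 0.3 | r = 0.5 |
|---|---|---|---|---|
| 23 | 0.845 SD | 0.851 | 0.816 | 0.741 |
| 60 | 0.516 SD | 0.515 | 0.494 | 0.449 |

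At 23 per group, power for a 0.5 SD difference is 38.2% by t-test, 40.4% at r = 0.3 and 47.3% at r = 0.5.

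**5. In numbers of women.** (0.845/0.816)² = 1.07 and 46 × 1.07 = 49; (0.845/0.741)² = 1.30 and 46 × 1.30 = 60. The net gain is worth about 3 to 14 women on 46.

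**6. Break-even.** With n = 23 and q = 1, variance is unchanged when (1 − r²) × (43/42) = 1, so r² = 1/43 and r is about 0.15. Below that there is no gain, but the loss is small (0.851 against 0.845 SD at r = 0.1).

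**7. Adding recruitment route (q = 2).** If route explains nothing beyond baseline pain, the bracket becomes 1 + 2/41 and df = 42. The detectable difference at 23 per group is then 0.826 SD at r = 0.3 and 0.750 SD at r = 0.5, and break-even moves to about r = 0.22. This is the least favourable case for that term.

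**The case against.** The strongest reply is that the plan is silent, not wrong. Linear regression is listed and can carry a baseline term, and the sensory-testing profile is already promised a role. That stands: the fault is under-specification, and a reader who infers a decision to ignore baseline pain goes further than the text.

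Other stronger readings are tempting and are not supported.
- *The change of form causes the loss of precision.* It does not. Adjustment needs only a pre-allocation measure correlated with the outcome, and a long-form score can be that measure. Identical scoring matters for change from baseline, and no change score for pain is stated.
- *There is no like-for-like pain baseline.* The documents list the items of neither form, so whether a common score can be built is open. All that can be said is that none is specified.
- *Pain is the stated pathway from technique to depression.* The plan examines pain by group and pain against EPDS, but sets out no mediation hypothesis, and the protocol calls postpartum pain a covariate on day 0-2 and at 6 weeks.

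It is also fair to say that the analysis paragraph does not define pain, which could include the hourly labor scales; that the correlation is assumed, and that mixing third-trimester and early-labor reports may lower it; and that a pilot meant to settle procedures does not turn on the precision of this comparison. These limit the importance of the point. They do not remove the case for naming the model, since the data are collected anyway and the cost is negligible.

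**Conclusion.** The point holds as a minor improvement. The STATISTICAL ANALYSIS PLAN specifies no baseline pain term for pain by group, although all participants supply a pre-allocation BPI. At 23 per group and an assumed correlation of 0.3 to 0.5, using it shrinks the detectable difference by about 3% to 12% ((0.845 − 0.816)/0.845 and (0.845 − 0.741)/0.845), slightly less once recruitment route is added. With a correlation below about 0.15 there is nothing to gain.

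The issue is precision only. A reader might infer that the unadjusted comparison is biased; allocation is randomised, so omitting the covariate does not bias it. The size rests wholly on the assumed correlation, which the pilot itself could estimate for a full trial.

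**What to change.** In the STATISTICAL ANALYSIS PLAN:
1. For BPI at day 0-2, 6 weeks and 3 months, replace the t-test with linear regression on assigned group, baseline BPI and recruitment route (third trimester versus early labor).
2. Name the one BPI score to be analysed. The long-form baseline score may be used as the covariate.
3. State that any change from baseline uses only a score computed the same way on the long and short forms.

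The cost is SAP wording and one or two degrees of freedom, with a slight loss of precision if the correlation proves very low. No new visit or instrument is needed.

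Two further changes are optional and do not form part of this fix. Moving the baseline to the short form would give up any items found only on the long form. Adding the cervical examination at epidural request as a covariate for the labor pain scales would rest on a prognostic value that the documents do not establish.

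### Non-responders are excluded by default and imputation is only reserved, so a woman who misses the 6-week survey contributes nothing to the primary EPDS comparison (minor, cheap to fix)

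*Combined protocol and SAP*

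**What the plan says.** The STUDY PROTOCOL section sets the default in its follow-up paragraphs: "Should a participant not respond to follow-up surveys at the specified time, we will exclude their data from analysis". The same sentence continues: "depending upon the volume and nature of such missing data", "we reserve the ability to impute missing data if MAR or MNAR". It names no imputation method, variables, threshold or sensitivity analysis.

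The specified time at 6 weeks is a window: "A margin of 7 days around the 6 week postpartum mark will be allowed for the patient to respond". The 3-month survey has the same 7-day margin.

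EPDS is planned at three times:
- **Baseline:** "At the first encounter, an assessment will include measurements of depression (EPDS"). Women recruited in early labor also complete the baseline surveys.
- **6 weeks:** the primary outcome.
- **3 months:** "At 3 months, we will assess breastfeeding (Y/N), Depression (EPDS").

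The STATISTICAL ANALYSIS PLAN section names linear regression of EPDS on treatment group, by group and across visits, together with t-tests and chi-squared tests. It has no missing-data rule, names no repeated-measures model and does not mention baseline adjustment. For the full trial it writes "With an optimistic estimated attrition of 15" per cent; for the pilot it calls attrition unknown. The pilot data that it lists for collection are screening, consent and refusal, crossover and feedback. Follow-up response is not on the list.

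**The concern.** Two things are at stake.

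First, the handling of missing primary-outcome values is left open until those values are known to be missing. The stated trigger cannot settle it. Observed data cannot distinguish MAR from MNAR, and the two call for different methods.

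Second, the default is a complete-case comparison at 6 weeks. It leaves out EPDS scores that the trial already plans to collect from the women it drops. It loses some precision, and it can be biased if non-response is related to EPDS and the relation differs by arm. The pilot is meant to settle procedures for a larger trial, so a weak default could be carried forward.

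**Working it through.** **The plan's own figures.** For 20% against 10%, two-sided 5%, 80% power, unpooled variance: (0.20×0.80 + 0.10×0.90) × (1.960 + 0.842)² / 0.10² = 196.2, so 197 per group, as stated. The enrolment figure follows from 197 × 1.15 = 226.6, so 227 per group. The 15% used below is therefore the plan's own.

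**How many women.** Pilot target 46: 46 × 0.15 = 6.9 without a 6-week EPDS, and 46 × 0.85 = 39.1 remaining (19.55 per group).

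**Assumptions for bias (none is in the documents).** EPDS is in SD units, with no true effect. Correlations are 0.5 (baseline with 6 weeks), 0.65 (6 weeks with 3 months) and 0.5 (baseline with 3 months). In one arm the probability of missing 6 weeks is p(z) = 1/(1 + exp(−(a + s·z))), where z is the EPDS score that drives non-response. The mean of p is 0.15, with s = 0.5 or 1.0 per SD (a = −1.819 or −2.048). In the other arm 15% are missing at random.

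**Complete-case bias, unadjusted.** Among responders the mean of the driver shifts by k = E[z·p(z)]/0.85, which integrates to 0.0726 (s = 0.5) or 0.1326 (s = 1.0). The 6-week difference shifts by r × k, where r is the driver's correlation with 6-week EPDS.

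**Completers adjusted for baseline EPDS.** The baseline slope is 0.5, so the remaining bias is (r − 0.5 × c) × k, where c is the driver's correlation with baseline:
- baseline-driven: (0.5 − 0.5 × 1) × k = 0
- 3-month-driven: (0.65 − 0.5 × 0.5) × k = 0.40k
- 6-week-driven: (1 − 0.5 × 0.5) × k = 0.75k

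**MAR model using baseline and 3-month EPDS from everyone.** These values come from a large simulation with 600,000 women per arm. The three cases are: none, half or all of the women who miss 6 weeks also miss 3 months.

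| Driver of non-response (one arm only) | Unadjusted complete case | Completers, baseline-adjusted | MAR model: none / half / all miss both |
|---|---|---|---|
| Baseline EPDS | 0.036–0.066 | about 0 | about 0 throughout |
| 3-month EPDS | 0.047–0.086 | 0.029–0.053 | about 0 / 0.01–0.02 / 0.03–0.05 |
| 6-week EPDS itself (MNAR) | 0.073–0.133 | 0.054–0.099 | 0.04–0.07 / 0.05–0.09 / 0.05–0.10 |

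Entries are absolute bias in SD. With the same pattern in both arms and no true effect, the bias is 0.

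**What non-responders' own scores add.** Compare the last two columns. There is no gain if baseline drives non-response. The gain is 0.03 to 0.05 SD if the 3-month score drives it and is observed, and nil if the same women miss both surveys. Under MNAR the reduction is partial.

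**Precision at 46 women (95% half-width).**
- Unadjusted: 1.96 × √(2/19.55) = 0.63 SD.
- Completers, baseline-adjusted: simulated standard error 0.281, so 1.96 × 0.281 = 0.55 SD.
- With non-responders' scores as well: 1.96 × 0.277 = 0.54 SD. As a check, the correlation of the 6-week and 3-month scores given baseline is (0.65 − 0.25)/0.75 = 0.533, and √(1 − 0.15 × 0.533²) = 0.978, a gain of about 2%.

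**Scale.** The largest bias is 0.133/0.627 = 21% of the half-width. Simulated coverage of the complete-case 95% interval at pilot size is 93% to 95%. At the SAP's maximum of 60 per group (51 responders each) the half-width is 1.96 × √(2/51) = 0.39 SD, and 0.133 is 34% of it.

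**If 15% is too low.** At an assumed 30% non-response, about 14 of 46 women are missing and k = E[z·p(z)]/0.70 = 0.143 or 0.253. The unadjusted bias then runs from 0.5 × 0.143 = 0.07 to 0.25 SD, against a half-width of 1.96 × √(2/16.1) = 0.69 SD.

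**The case against.** The strongest reply is that most of the benefit comes from a simpler remedy. Adjusting completers for baseline EPDS removes baseline-driven bias and narrows the half-width from 0.63 to 0.55 SD without any data from non-responders. This stands. Those gains belong to covariate adjustment and should not be credited to recovering non-responders.

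Second, the protocol does reserve imputation, which could use the baseline and 3-month scores, and the SAP does plan a regression of EPDS across visits. A reader might infer that non-responders' scores can never be used. The documents do not support that; the claim is limited to the default. But neither sentence commits to a method, and ordinary linear regression does not bring back women whom the exclusion rule has removed.

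Third, this is a pilot at 10% of the full sample, with unknown attrition and a protocol reviewed every 5 patients. Deferring the choice is less serious here than in a confirmatory trial. This also stands, and it lowers the severity. It does not remove the point, because settling procedures is what the pilot is for.

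Two further readings are tempting. One is that a woman who misses any survey loses all her data. The text more naturally refers to the missed survey, since the sentence goes on to discuss the missing data it creates. The other is that late answers are collected and then thrown away. Contact is flexible ("Interactions with participants will occur in person, electronically (email), or by phone"), but the documents do not say that surveys are accepted after the window. Neither reading is relied on here.

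**Conclusion.** The point holds in a limited form. The default rule excludes non-responders, the alternative is unspecified and chosen after the fact, and the SAP does not override either. The women affected number about 7 of 46 at the plan's 15%.

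A reader might infer that the 6-week result will be biased. The documents do not support that. Every non-zero bias above rests on an assumed relation between non-response and EPDS in one arm only, and on assumed correlations. Even then the unadjusted bias at 15% is about 0.04 to 0.13 SD against a half-width of about 0.63 SD. Nor does the working support the inference that non-responders' scores would transform the analysis: they add about 2% precision, help with bias only when non-response tracks an observed 3-month score, and reduce MNAR bias only in part.

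Severity: minor, a cheap improvement. Confidence in the reading of the text is high; confidence in the size is moderate, because the rates and correlations beyond 15% are assumptions.

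**What to change.** Replace the exclusion sentence with:

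> A missed survey removes only that survey. The 6-week EPDS comparison includes all randomised women with any observed EPDS, in the group assigned, adjusted for baseline EPDS, using a likelihood-based repeated-measures model (or multiple imputation including arm, baseline and 3-month EPDS) under MAR, with one pre-specified delta-adjusted sensitivity analysis for MNAR.

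Keep the 7-day window as it is. Add 6-week and 3-month response by arm to the feasibility data listed in the STATISTICAL ANALYSIS PLAN section, since the full trial's attrition allowance depends on it.

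The cost is a change of SAP wording, slightly more analysis work, and reliance on an MAR model in a small sample (about 39 women with a 6-week value). The part of the gain that comes from the 3-month score is nil for women who miss both surveys. No extra patients, visits or measurements are needed.
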